4.3. Exclusion Criteria

Subjects who meet *any* of the following exclusion criteria are not to be enrolled in this study.

- 1) An opportunistic illness indicative of stage 3 HIV diagnosed within the 30 days prior to screening (refer to [Appendix 6](#))
- 2) Subjects with cirrhosis, compensated or decompensated (e.g., ascites, encephalopathy, or variceal bleeding)
- 3) Have been treated with immunosuppressant therapies or chemotherapeutic agents within 3 months of study screening, or expected to receive these agents or systemic steroids during the study (e.g., corticosteroids, immunoglobulins, and other immune- or cytokine-based therapies)
- 4) Current alcohol or substance use judged by the Investigator to potentially interfere with subject study compliance
- 5) Malignancy within 5 years of screening other than cutaneous Kaposi's sarcoma, completely resected non-melanoma skin cancer (basal cell carcinoma or non-invasive cutaneous squamous carcinoma), or completely resected carcinoma in-situ of the cervix (CIN 3) or anus (AIN 3). A prior malignancy treated with curative therapy and for which there has been no evidence of disease for at least five years prior to screening is allowed.
- 6) Active, serious infections (other than HIV-1 infection) requiring parenteral antibiotic or antifungal therapy within 30 days prior to Day 1

- 7) Participation in any other clinical trial, including observational studies, without prior approval from the sponsor is prohibited while participating in this trial
- 8) Use of an investigational drug other than GS-9131 or BIC or TAF
- 9) Any other clinical condition or prior therapy that, in the opinion of the Investigator, would make the subject unsuitable for the study or unable to comply with the dosing requirements
- 10) Known hypersensitivity to investigational medicinal products GS-9131, BIC, TAF, DRV, RTV, their metabolites, or formulation excipient
- 11) Acute hepatitis in the 30 days prior to randomization
- 12) Subjects with chronic hepatitis B virus infection are not permitted to participate.
 - For the purposes of this study, chronic HBV infection is defined as: Positive HBV surface antigen and negative HBV surface antibody, regardless of HBV core antibody status
 - Positive HBV core antibody and negative HBV surface antibody, regardless of HBV surface antigen status, at the screening visit
- 13) Subjects with chronic HCV infection requiring HCV therapy during the course of the study. Subjects with chronic HCV are eligible if the investigator does not anticipate treatment for HCV.
- 14) Active tuberculosis infection
- 15) Subjects receiving ongoing therapy with any of the medications listed in Section 5.4, including drugs not to be used with BIC, TAF, DRV and RTV.

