Diagnosis and Main Eligibility Criteria:	
HIV-1 infected subjects who meet the following criteria:
 
• Non-pregnant/non-lactating females, ≥ 18 years of age at Screening. Females of childbearing potential (as defined in Appendix 7) must have a negative serum pregnancy test at Screening and Day 1.• Subjects of childbearing potential who engage in heterosexual intercourse must agree to use protocol-specified method(s) of contraception as described in Appendix 7.• Estimated glomerular filtration rate (eGFR) (Cockcroft-Gault equation) ≥ 70 mL/min• Currently taking a failing ARV regimen that contains an NRTI• HIV-1 RNA ≥ 500 copies/mL at Screening• CD4 > 100 cells/μL at Screening• Have a screening genotype showing at least the following resistance mutation profile (a local genotype at the Screening visit is acceptable for enrollment upon review by the Sponsor):
— K65R or— at least 3 TAMs; TAMs are defined as: M41L, D67N, K70R, L210W, T215F/Y, or K219Q/E/N/R in reverse transcriptase (RT) or— Q151M— and at least one primary resistance mutation to an NNRTI• No prior or current ARV regimens containing integrase inhibitor (INSTI) or protease inhibitor (PI)• No evidence of chronic viral hepatitis B or C infection. Note: Subjects with positive hepatitis C virus (HCV) antibody and without detectable HCV RNA are permitted to enroll. 
No evidence of active AIDS-related opportunistic infection, including tuberculosis.

Study Procedures/
Frequency:

At Screening, laboratory analyses (hematology, chemistry, urinalysis, and serum pregnancy test [for females of childbearing potential]), HIV-1 RNA, cluster determinant 4 (CD4) cell count, vital signs, electrocardiogram (ECG), complete physical examination, and eGFR will be performed. HIV-1 protease, and reverse transcriptase genotype/phenotype, and hepatitis B virus (HBV) and HCV serologies will be analyzed.

Part 1:

Sentinel Cohort 1 (GS-9131 60 mg plus Current Failing Regimen)

Following Screening and Day 1 (baseline) visits, subjects will be required to visit the clinic daily on Days 2-11. All study medication will be delivered by DOT on Days 1-10.

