6.8.1. Blood Samples

- **Blood samples will be collected for the following laboratory analyses** (Refer to Appendix 2, and Appendix 3):
 - Serum pregnancy test (females of childbearing potential only). If the test is positive, the subject will not be enrolled (**Screening and Day 1 only**). Positive urine pregnancy tests will be confirmed with a serum test.
 - Follicle-stimulating hormone (FSH) (females who have ceased menstruating for greater than or equal to 12 months but do not have documentation of ovarian hormonal failure) Female subject post-menopausal for less than two year, if FSH < 40 mIU/ mL a serum pregnancy test will be required (**Screening only**)
 - Chemistry profile: alkaline phosphatase, AST, ALT, total bilirubin, direct and indirect bilirubin, total protein, albumin, CPK, bicarbonate, blood urea nitrogen (BUN), calcium, chloride, creatinine, glucose, phosphorus, magnesium, potassium, sodium, uric acid, amylase (reflex lipase testing is performed in subjects with total amylase > 1.5 × ULN)
 - Metabolic profile: Fasting (no food or drinks, except water, at least 8 hours prior to blood collection) glucose and lipid panel (total cholesterol, HDL, direct LDL, and triglycerides) collected at **Part 1 – Day 1, Part 2 – Day 1, Weeks 12** CCI [REDACTED].
 - If the subject has not fasted prior to the visit, the visit may proceed, but the subject must return within 72 hours in a fasted state to draw blood for the metabolic assessments

— eGFR according to the Cockcroft-Gault formula:

$$\text{Female: } \frac{(140 - \text{age in years}) \times (\text{wt in kg}) \times 0.85}{72 \times (\text{serum creatinine in mg/dL})} = \text{CLcr (mL/min)}$$

$$\frac{(140 - \text{age in years}) \times (\text{wt in kg})}{72 \times (\text{serum creatinine in } \mu\text{mol/L})} \times 0.85 = \text{CLcr (mL/sec)}$$

— Hematology profile: complete blood count (CBC) with differential and platelet count.

— CD4 cell count and percentage

— Plasma HIV-1 RNA

— HBV blood panel: Hepatitis B virus surface antigen serology (HBsAg), Hepatitis B virus surface antibody (HBsAb) and Hepatitis B virus core antibody (HBcAb)

The following tests will be conducted by the central laboratory if the following criteria are met:

- If positive HBsAg, reflex testing for plasma HBV DNA, Hepatitis B virus e-antigen (HBeAg) (if negative, reflex Hepatitis B virus e-Antibody [HBeAb]), and quantitative HBsAg.

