- If positive HBcAb with negative HBsAg and negative HBsAb: reflex testing for plasma HBV DNA (if positive, reflex HBeAg). If HBeAg is performed and found to be negative, reflex HBeAb

If the subject meets the definition of HBV infection at screening, they will not be enrolled. If the subject meets the definition of HBV infection during the study, HBV treatment and study continuation must be discussed with the Gilead Medical Monitor.

— Hepatitis C Virus (HCVAb) serology. Subjects who are HCVAb positive will have a HCV RNA test performed.

■ [REDACTED]

— Plasma, CCI [REDACTED] and serum storage sample for safety, or virology testing

— HIV-1 genotype/phenotype testing for subjects with virologic failure (**Screening, Days 1 15 (Sentinel Cohort 2)**)

— Sparse PK Samples:

- Single Anytime PK Sample: collected without regard to time of dosing (**Part 2 - Weeks 2, 8 and 24**)
- Timed PK Sample: collected at predose and one within 15 minutes-4 hours post dose (**Part 2 - Weeks 4, 12, and 18**)

— Intensive PK

- Plasma samples will be collected on **Day 10** for Sentinel Cohort 1 and **Day 14** for Sentinel Cohort 2 and Randomized Cohort.
- Prior to the administration of study drug, a predose (< 5 minutes prior to dosing) will be collected. Subjects will then take an observed dose of study drug at the clinic. Additional blood samples will be collected at 0.5, 1, 1.5, 2, 3, 4, 6, 8, and 24 hour post dose.

— PBMC samples will be collected on **Day 10 for Sentinel Cohort 1 and Day 14 for Sentinel Cohort 2 and Randomized Cohort**: Predose (<5 minutes prior to dosing), 1, 2, 6 and 24 hours post dose

CCI [REDACTED]

[REDACTED]

— Subjects must be instructed to not to take their study drugs on the morning of their visit. Prior to the administration of study drug, a predose (< 5 minutes prior to dosing) plasma blood sample will be collected. Subjects will then take an observed dose of study drug at the clinic. Additional plasma blood samples will be collected at 0.5, 1, 1.5, 2, 3, 4, 6, and 8 hours post dose. PBMC PK samples will be collected at predose (<5 minutes prior to dosing), 1, 2, and 6 hours post dose.

CCI [REDACTED]

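### Both limbs of the hepatitis B exclusion require a negative surface antibody, so a subject positive for surface antigen and surface antibody is not excluded by criterion 12, even with detectable HBV DNA

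*Protocol*

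**What the plan says.** Protocol Section 4.3, exclusion 12, opens with a general bar: "Subjects with chronic hepatitis B virus infection are not permitted to participate". It then defines chronic HBV infection for study purposes by two limbs:

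- Limb 1: "Positive HBV surface antigen and negative HBV surface antibody, regardless of HBV core antibody status".
- Limb 2: "Positive HBV core antibody and negative HBV surface antibody, regardless of HBV surface antigen status, at the screening visit".

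Section 6.8.1 schedules surface antigen (HBsAg), surface antibody (HBsAb) and core antibody (HBcAb). The reflex rule reads "If positive HBsAg, reflex testing for plasma HBV DNA", and it adds e-antigen and quantitative HBsAg. It applies whatever the HBsAb result. A second reflex rule orders HBV DNA when HBcAb is positive and both HBsAg and HBsAb are negative.

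The consequence is then stated: "If the subject meets the definition of HBV infection at screening, they will not be enrolled". If the same definition is met later, HBV treatment and continuation have to be discussed with the sponsor's medical monitor.

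The synopsis eligibility list, repeated in SAP Section 1.2, has "No evidence of chronic viral hepatitis B or C infection". Its note on antibody-positive, RNA-negative subjects concerns hepatitis C only. Nothing there qualifies hepatitis B.

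**The concern.** An eligibility rule should give effect to the requirement it stands for. Here the requirement is the absence of chronic hepatitis B, but the operative definition depends on HBsAb being negative. One serological pattern with a positive surface antigen therefore falls outside it.

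The protocol also orders a direct test for virus in exactly that pattern and attaches no consequence to the result. A site could hold a positive HBV DNA report, find that neither limb is met, and have no HBV rule telling it what to do. Two sites could decide differently and both be following the text.

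The gap carries into follow-up. The on-study discussion with the medical monitor is triggered by the same definition, so a repeat panel (Appendix 3 schedules one at Part 2 Day 1 and at Week 24) showing the same pattern would not trigger it.

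**Working it through.** The plan gives no figure to reproduce; the check is logical.

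**Inputs.** Limbs 1 and 2 from Protocol 4.3 (12); the two reflex rules and the enrolment bar from 6.8.1.

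**Rules as written.**
- Excluded by 12 = (HBsAg+ and HBsAb−) or (HBcAb+ and HBsAb−).
- Reflex DNA ordered = HBsAg+, or (HBcAb+ and HBsAg− and HBsAb−).

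| HBsAg | HBsAb | HBcAb | Limb 1 | Limb 2 | Excluded by 12 | Reflex DNA |
|---|---|---|---|---|---|---|
| + | − | + | yes | yes | yes | yes |
| + | − | − | yes | no | yes | yes |
| + | + | + | no | no | **no** | yes |
| + | + | − | no | no | **no** | yes |
| − | − | + | no | yes | yes | yes |
| − | − | − | no | no | no | no |
| − | + | + | no | no | no | no |
| − | + | − | no | no | no | no |

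**Counts.** Splitting each row by HBV DNA (+ or −) gives 8 × 2 = 16 combinations.
- HBsAg-positive: 4 rows × 2 = 8.
- Of these, excluded: 2 rows × 2 = 4. Not excluded: 2 rows × 2 = 4, of which 2 have positive DNA.
- Limb 2 does not close the gap, because it also needs HBsAb−.

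**Role of the DNA result.** Reflex DNA is ordered in 5 rows. In 3 of them the serology already excludes the subject. The other 2 are the HBsAg+/HBsAb+ rows, the only ones where the result could change eligibility. It does not, because DNA appears in neither limb and the enrolment bar in 6.8.1 names no DNA result.

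**Cause.** As an illustration, not a proposed rule: if a positive HBsAg counted whatever the HBsAb result, 0 of the 8 combinations would fall outside the definition, against 4 of 8 as written. The HBsAb condition alone produces the gap.

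**Reading assumptions.** The limbs are taken as alternatives. Were they joint conditions, negative HBsAb would still be needed and the definition would be narrower still. The definition that 6.8.1 refers to is taken to be that of exclusion 12, the only one in the protocol.

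**The case against.** The best defence is that the synopsis lists main criteria in short form and 4.3 supplies the working definition; a summary and a definition need not conflict. The general bar in exclusion 12 is also still there, and other criteria apply: exclusion 9 covers "Any other clinical condition or prior therapy that, in the opinion of the Investigator, would make the subject unsuitable for the study", exclusion 11 covers acute hepatitis in the preceding 30 days, and inclusion 10 caps AST and ALT at 2 × ULN. The investigator would see the DNA result.

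Part of this stands. Such a subject is not necessarily enrolled; the documents support only that criterion 12 does not exclude her. But none of the other criteria is a hepatitis B rule, and exclusion 9 is discretionary. Treating the synopsis as shorthand still leaves the DNA result without a role, and 6.8.1 itself treats any positive HBsAg as needing HBV work-up.

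A reader might infer larger consequences that the documents do not support:

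- **Sentinel stopping rule.** One might argue that a hepatitis flare after the failing regimen is withdrawn would count toward the two-subject laboratory trigger. Section 6.5.1 confines that trigger to Part 1, when Section 5.3 keeps the current antiretrovirals going; withdrawal comes only at Part 2. The synopsis version omits the Part 1 limit, but it is the shorter statement.
- **Part 2 without TAF.** Only Sentinel Cohort 1 has a Part 2 regimen lacking TAF, which Section 1.8.4 notes is approved for chronic hepatitis B. Section 1.2.3.3 reports that cohort as already dosed, with 11 subjects and one progressing to Part 2. Later cohorts receive TAF in Part 2, so rewording the criterion would not change that exposure.

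**Conclusion.** Wrong as written, low severity. By its wording, exclusion 12 fails to exclude HBsAg-positive, HBsAb-positive subjects, including those with detectable HBV DNA. This does not agree with the synopsis and SAP requirement, or with the protocol's own reflex testing. The same definition leaves the same gap on study.

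The size is 4 of 8 HBsAg-positive marker combinations, which counts patterns and not people. A reader might want to multiply the planned 68 subjects by assumed prevalences, but the documents give neither the rate of HBsAg positivity nor how often HBsAb accompanies it. The number affected cannot be estimated from them. The pattern is probably rare, and the case rests on the disagreement between the texts and on the low cost of removing it.

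**What to change.** Reconcile the synopsis, Section 4.3 (12), Section 6.8.1 and SAP Section 1.2 into one hepatitis B definition, used both for screening and for the on-study discussion with the medical monitor. It should state explicitly:

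- how the HBsAg+/HBsAb+ pattern is classified;
- how a positive reflex HBV DNA result is classified, and what follows from it.

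The aim is that a subject with evidence of chronic hepatitis B is not let in by the wording of the limbs. Which serological or DNA rule achieves that is a clinical decision for the sponsor.

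The serology and reflex DNA are already scheduled, so no new test is needed. The cost is the rewording and a rare additional screen failure.

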5. INVESTIGATIONAL MEDICINAL PRODUCTS

5.1. Randomization, Blinding and Treatment Codes

It is the responsibility of the investigator to ensure that the subject is eligible for the study prior to enrollment. Subjects will be assigned a screening number at the time of consent.

Subjects who meet criteria will first be enrolled in the Sentinel Cohorts. The Sentinel Cohort 1 is an open-label cohort that will enroll 10 HIV-1 positive subjects to receive GS-9131 60 mg plus their current failing regimen for 10 days. The Sentinel Cohort 2 is an open-label cohort that will enroll up to 10 HIV-1 positive subjects to receive GS-9131 180 mg plus their current failing regimen for 14 days. Randomization and dosing of the Randomized Cohort of Part 1 will begin after the Day 15 safety, efficacy, and available PK data from the Sentinel Cohort 2 are reviewed.

Once eligibility has been confirmed for the Randomized Cohort and prior to or during the Part 1 Day 1 visit, the Investigator or designee will randomize the subject using the Interactive Web Response System (IWRS). Once a subject number has been assigned to a subject, it will not be reassigned to any other subject. The subject number assignment and randomization may be performed up to 3 days prior to the in-clinic Part 1 Day 1 visit provided that all screening procedures have been completed and subject eligibility has been confirmed. The Investigator must have results from genotype testing and confirmed eligibility before proceeding with subject randomization.

The IWRS will assign study drug bottle numbers of blinded GS-9131 or PTM at each study visit for each subject. At the beginning of Part 2, IWRS will assign GS-9131 + BIC + TAF.

5.1.1. Procedures for Breaking Treatment Codes

In the event of a medical emergency where breaking the blind is required to provide medical care to the subject, the investigator may obtain treatment assignment directly from the IWRS system for that subject. Gilead recommends but does not require that the investigator contact the Gilead medical monitor before breaking the blind. Treatment assignment should remain blinded unless that knowledge is necessary to determine emergency medical care for the subject. The rationale for unblinding must be clearly explained in source documentation and on the electronic case report form (eCRF), along with the date on which the treatment assignment was obtained. The investigator is requested to contact the Gilead medical monitor promptly in the event of any treatment unblinding.

Blinding of study treatment is critical to the integrity of this clinical trial and therefore, if a subject's treatment assignment is disclosed to the investigator, the subject will have study treatment discontinued. All subjects will be followed until study completion unless consent to do so is specifically withdrawn by the subject.

Gilead Pharmacovigilance and Epidemiology (PVE) may independently unblind cases for expedited reporting of suspected unexpected serious adverse reactions (SUSARs).

5.2. Description and Handling of Study Drug

5.2.1. Formulation

5.2.1.1. GS-9131 tablets, 30 mg

GS-9131 tablets, 30 mg, are round, film-coated white, plain-faced tablets. In addition to the active ingredient, the GS-9131 tablets contain the following inactive ingredients: lactose anhydrous, microcrystalline cellulose, croscarmellose sodium, magnesium stearate, polyvinyl alcohol, polyethylene glycol, talc and titanium dioxide.

5.2.1.2. Bictegravir tablets, 30 and 75 mg

Bictegravir tablets, 30 mg and 75 mg are round, film-coated yellow, plain-faced tablets. In addition to the active ingredient, the bictegravir tablets contain the following inactive ingredients: lactose monohydrate, microcrystalline cellulose, crospovidone, sodium stearyl fumarate, polyvinyl alcohol, titanium dioxide, polyethylene glycol, talc, and iron oxide yellow.

5.2.1.3. Prezista[®] (DRV)

Information regarding the formulation of commercially available Prezista[®] (DRV) 800 mg tablets can be found in the package insert from the USPI or summary of product characteristics.

5.2.1.4. Norvir[®] (RTV)

Information regarding the formulation of commercially available Norvir[®] (RTV) 100 mg tablets can be found in the package insert from the USPI or summary of product characteristics.

5.2.1.5. Tenofovir alafenamide tablets (Vemlidy, TAF)

Tenofovir alafenamide (TAF) tablets are round, film-coated yellow tablets debossed with “25” on one side of the tablet and “GSI” on the other side. In addition to the active ingredient, the tablet cores contain lactose monohydrate, microcrystalline cellulose, croscarmellose sodium, magnesium stearate, polyvinyl alcohol, titanium dioxide, polyethylene glycol, talc, and iron oxide yellow.

5.2.1.6. Placebo-to-match GS-9131 tablets

Placebo-to-match (PTM) GS-9131 tablets 30 mg, are round, film-coated white, plain-faced tablets. The PTM GS-9131 tablets contain the following inactive ingredients: lactose monohydrate, microcrystalline cellulose, croscarmellose sodium, magnesium stearate, polyvinyl alcohol, polyethylene glycol, talc and titanium dioxide.

5.2.2. Packaging and Labeling

GS-9131 tablets, 30 mg, and PTM are packaged in white, high density polyethylene (HDPE) bottles. Each bottle contains 30 tablets, silica gel desiccant and polyester packing material. Each bottle is enclosed with a white, continuous thread, child-resistant polypropylene screw cap with an induction-sealed and aluminum-faced liner.

Bictegravir tablets, 30 mg and 75 mg, are packaged in white HDPE bottles. Each bottle contains 30 tablets, and polyester packing material. Each bottle is enclosed with a white, continuous thread, child-resistant polypropylene screw cap with an induction-sealed and aluminum-faced liner.

Tenofovir alafenamide (TAF) 25 mg tablets are packaged in white HDPE bottles. Each bottle contains 30 tablets, silica gel desiccant and polyester packing material. Each bottle is enclosed with a white, continuous thread, child-resistant polypropylene screw cap with an induction-sealed and aluminum-faced liner.

Commercially available Prezista and Norvir will be used for the study.

GS-9131, BIC, TAF, Prezista and Norvir to be distributed to centers in participating countries shall be labeled to meet applicable requirements of the US FDA, EU Guideline to Good Manufacturing Practice - Annex 13 (Investigational Medicinal Products [IMPs]), and/or other local regulations.

5.2.3. Storage and Handling

GS-9131, PTM GS-9131, BIC and TAF tablets should be stored at controlled room temperature of 25°C (77°F); excursions are permitted between 15°C and 30°C (59°F and 86°F), or as otherwise specified on the label. Storage conditions are specified on the label. Until dispensed to the subjects, all bottles of study drugs should be stored in a securely locked area, accessible only to authorized site personnel.

To ensure stability and proper identification, study drug(s) should not be stored in a container other than the container in which they were supplied. Keep the bottle tightly closed to protect from moisture.

Consideration should be given to handling, preparation, and disposal through measures that minimize drug contact with the body. Appropriate precautions should be followed to avoid direct eye contact or exposure when handling.

Commercial Prezista and Norvir will be used for the study. Further information regarding storage and handling are available in the Prescribing Information.

